This distribution corresponds to a standardized effect of 0.34 for the primary analysis. Based on these data, the fixed sample size for a non-adaptive design requires a total of 376 patients (188/arm) to have 90% power at an alpha of 5% (Wilcoxon-Mann-Whitney test); We add additional 184 patients for the adaptive design to reach a maximum sample size of 560. We will conduct two interim analyses when we reach the number of patients at 200 and 380. Through extensive simulation studies, we have shown that with 560 patients in total for the adaptive design, we will have around 91% power to test for a standardized effect size of 0.34 in the overall population (assuming homogeneous EVT effect across six disjoint groups) by controlling an overall (one-sided) Type I error rate at 2.5%.

Efficacy and futility bound At each analysis (two interim analyses and the final analysis), an efficacy bound will be set to decide if the study should be stopped for efficacy while controlling the overall (one-sided) Type I error rate at 2.5%. At each interim analysis, a futility bound will be set to decide if the study should continue recruitment in the overall group, shift accrual and testing to a subgroup, or stop the trial entirely. When the futility bound is crossed and the optimal subgroup is selected, the maximum analyzed sample size will not be fixed but a random variable (smaller than the fixed maximum sample size 560). Due to the reduction in the maximum number of patients available for analysis at the end of the study, our design allows

an easier futility stop after subgroup selection. Further details regarding efficacy and futility bounds at interim and final analyses is provided in Appendix B.

First interim analysis (n=200 randomized and completed 90-day follow-up): The null hypothesis is tested in the entire patient cohort:

1. If neither efficacy nor futility bound is crossed, the trial continues enrollment to the 2nd interim analysis.
2. If the efficacy bound is crossed, the trial stops and efficacy is declared in the overall cohort.
3. If the futility bound is crossed, the optimal subgroup is selected based on the GLR statistic and the null hypothesis is tested in this selected subgroup:
 - 3.1. If neither bound is crossed, the trial will continue with enrollment limited to the selected subgroup
 - 3.2. If the efficacy bound is crossed, the trial stops and efficacy is declared in the selected subgroup

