 - 3.3. If the futility bound is crossed, the trial stops for futility.

Note: the futility bound is relaxed as described above, based on the expected maximum number of patients in the trial at completion (i.e. 560 minus the number of patients already enrolled in the groups that will no longer be open for enrollment).

Second interim analysis (n=380 randomized and completed 90 day follow-up): After the first interim analysis, the trial proceeds to this stage under two scenarios: (1) continuing enrollment in the overall population (i.e., option 1 above) and (2) limiting enrollment to a selected subgroup (i.e., option 3.1 above). When scenario (1) happens, the testing at the 2nd interim analysis is identical to the first interim analysis. When scenario (2) happens, the null hypothesis is tested in that selected subgroup:

1. If neither bound is crossed, the trial continues to the final analysis with an enrollment of $560-380=180$ additional patients limited to the selected subgroup

2. If the efficacy bound is crossed, the trial stops and efficacy is declared in the selected subgroup
3. If the futility bound is crossed, the trial stops for futility.

Final analysis (n=560 randomized and completed 90-day follow-up): After the 2nd interim analysis, the trial proceeds to the final stage under two scenarios: (1) continuing enrollment in the overall population and (2) limiting enrollment to a selected subgroup.

When scenario (1) happens, the null is tested in the overall population:

1. If the efficacy bound is crossed, EVT is declared efficacious in the overall population.
2. If the efficacy bound is not crossed, the optimal subgroup is selected and the null is tested in that group:
 - 2.1. If the efficacy bound is crossed, EVT is declared efficacious in that subgroup
 - 2.2. If the efficacy bound is not crossed, EVT will be declared of no benefit.

When scenario (2) happens, that is, limiting enrollment to a subgroup (either selected at the 1st or 2nd interim analyses), the null hypothesis is tested in that selected subgroup only. Efficacy or lack thereof will be declared as per options 2.1 and 2.2 above.

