Operating characteristics of the adaptive design: We have conducted simulations (5000 simulated trials) to evaluate the performance of the adaptive design (max n=560) and compare it to a traditional fixed sample-size design (fixed n=560) under various scenarios (see **Table 3**, below). For the simulations the effect size is expressed as a standardized effect with normal approximation, where a standardized effect of 0.32 or 0.30 corresponds to a conservative projected effect of EVT (anticipated effect 0.34; see section of Power and sample size considerations). We assume that we will observe the number of patients in G1A, G1B, G2A, G2B, G3A, G3B with 14%, 6%, 14%, 6%, 42%, and 18%, respectively.

Scenario	Standardized effect in groups G1A, G1B, G2A, G2B, G3A, G3B							Average standar d. effect	Adaptive Design		Fixed Design	
									Average No. randomized	Power	Number randomized	Power
#0	0	0	0	0	0	0	0	0	426	2.0%	560	2.5%
#1	0.32	0.32	0.32	0.32	0.32	0.32	0.32	0.32	376	86.0%	560	95.8%
#2	0.3	0.3	0.3	0.3	0.3	0.3	0.3	0.3	393	81.1%	560	93.3%
#3	0.4	0.4	0.4	0.4	0	0	0.16	0.16	500	74.1%	560	45.7%
#4	0.4	0.4	0.4	0.4	-0.1	-0.1	0.1	0.1	502	78.5%	560	21.2%
#5	0.4	0.4	0.3	0.3	0	-0.1	0.122	0.122	513	67.1%	560	29.2%
#6	0.5	0.5	0	0	0	0	0.1	0.1	503	70.6%	560	21.2%
#7	0.5	0	0	0	0	0	0.07	0.07	503	60.5%	560	12.8%

Table 3. Under the null (Scenario #0), the adaptive design controls the total Type 1 error below 2.5%, stops early for futility 59.1% of the time, and the average number of randomizations is 426. If the effect is uniform across cells at 0.32 (scenario #1), the fixed-sample design is optimal, but the adaptive design results in only a small loss of power (from 95.8% to 86.0%), but reduced the expected sample size (from 560 to 376). We observed similar findings when the effect is uniform across cells at 0.3 (scenario #2). The adaptive design performs much better (higher power and smaller expected sample size) than the fixed-sample design when the effect size distribution across the subgroups is in accord with the biological assumptions (scenarios #3, #4 and #5). If the effect is concentrated only in Group 1 (scenario #6) or Group 1A (scenario #7), the adaptive design maintains power (70.6% in scenario #6 and 60.5% in scenario #7) while the conventional design collapses (21.2% power in scenario #6 and 12.8% in scenario #7).

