6.4. Feasibility of enrollment

The study is planning to involve 30 high volume centers with volumes of 150-200 thrombectomies/site/year. Based on SELECT data, roughly 20% of the patients have unfavorable imaging profiles on either CT or CTP, with ~30 patients/site/year eligible to participate in the study. Assuming 50% of the patients consenting to participate in the study and at 30 sites coming onboard in a gradual fashion, the study will complete the enrollment target (560 patients) in nearly 2 years.

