Under our design setting (maximum sample size $N=560$ and conducting interim analysis at $N=200$ and $N=380$ with type I error at 0.025 and power at 0.9), we obtain $b = 2.604$, $\tilde{b} = -1.897$, $c = 2.772$ for our efficacy and futility boundaries. We assume θ to be the projected treatment effect given the maximum sample size for testing the hypothesis: $H_0: P(Y \leq X) = \frac{1}{2}$, $H_A = P(Y \leq X) = \frac{1}{2} + \theta$ using the fixed-sample-size test and is calculated as $\frac{(Z_{1-\alpha} + Z_{1-\beta})}{\sqrt{3N}} = 0.0791$. Here, Y denotes the Rankin score in the medical management group and X denotes the Rankin score in the endovascular group. The rationale of this set-up is detailed in section 3.1 of Lai et al (2014).

Reference

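### Table 3 leaves out patients randomised but still in 90-day follow-up at each interim, so it understates average sample size and overstates power in scenarios #3 to #7

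*Combined protocol and SAP*

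**What the plan says.** Section 6.1 sets the first look at "n=200 randomized and completed 90-day follow-up" and the second at "n=380 randomized and completed 90 day follow-up". If the overall futility bound is crossed at the first look and neither bound is crossed in the chosen subgroup, "the trial will continue with enrollment limited to the selected subgroup". If the whole population is still being recruited at the second look, "the testing at the 2nd interim analysis is identical to the first interim analysis", so a subgroup can also be selected for the first time there.

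Table 3 reports the average number randomised and the power for a maximum of 560, and its caption says the design "reduced the expected sample size (from 560 to 376" in scenario #1. Section 6.4 expects that "the study will complete the enrollment target (560 patients) in nearly 2 years", with 30 sites, about 30 eligible patients per site per year and 50% consenting. Enrollment holds are described for safety triggers (sections 9 and 10) and for poor image quality at a site (section 5), but not for the efficacy looks.

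On futility after selection, the section 6.1 note relaxes the bound using "560 minus the number of patients already enrolled in the groups that will no longer be open for enrollment". Appendix B gives one value, theta = 0.0791, described as "the projected treatment effect given the maximum sample size for testing the hypothesis".

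**The concern.** The primary endpoint is read at 90 days. When the 200th or 380th patient completes follow-up, everyone randomised in the preceding 90 days is already in the trial but cannot be analysed. This has two consequences.

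- **Sample size.** Those patients count as randomised even if the trial stops at that look, so early stopping saves fewer patients.
- **Power under enrichment.** Before a subgroup has been selected, the overrun comes from all six groups. It uses places under the cap of 560 that would otherwise go to the selected subgroup.

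Table 3 is the stated justification for choosing this design over a fixed design of 560. If it assumes outcomes are known immediately, its sample-size saving and its power where benefit is confined to subgroups are more favourable than the design as written would deliver.

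**Working it through.** **Inputs**

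- Appendix B: b = 2.604, futility bound -1.897, c = 2.772.
- Section 6.1: looks at 200, 380 and 560; group shares 14/6/14/6/42/18%; the Table 3 effects.
- Section 3.4 (remote consent and randomisation): 1:1 allocation.

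**Check of theta.** (1.960 + 1.2816)/sqrt(3 x 560) = 3.2415/40.99 = 0.0791, as stated. Under the relaxed rule, N is 560 minus patients in closed groups. For example, selecting Group 1 (20% of patients) at the first look closes about 160 patients, leaving N = 400 and theta = 3.2415/sqrt(1200) = 0.0936.

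**Overrun from section 6.4**

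- Average accrual: 560/2 = 280 per year; 280 x 90/365 = 69.
- All sites open: 30 x 30 x 50% = 450 per year; 450 x 90/365 = 111.
- Because sites open gradually, 35 at the first look is used as a lower assumption. The low case is 35 then 70 and the high case is 70 then 111.

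**Simulation.** The rank-sum statistic was applied to normal outcomes, with the largest-Z subgroup selected, the relaxed theta used after selection, and 10,000 trials per scenario. Overrun is drawn from all groups until a subgroup is chosen. After that it is subgroup-only and scaled to the subgroup's share. Total randomised is capped at 560.

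Average N / power (%):

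| Scenario | Stated | No lag | Overrun 35 then 70 | Overrun 70 then 111 |
|---|---|---|---|---|
| #1 | 376 / 86.0 | 373 / 87.0 | 412 / * | 438 / * |
| #2 | 393 / 81.1 | 395 / 81.5 | 425 / * | 452 / * |
| #3 | 500 / 74.1 | 498 / 73.8 | 514 / 73.0 | 523 / 70.3 |
| #4 | 502 / 78.5 | 501 / 78.8 | 514 / 76.0 | 523 / 73.3 |
| #5 | 513 / 67.1 | 508 / 67.9 | 519 / 65.2 | 527 / 62.3 |
| #6 | 503 / 70.6 | 500 / 70.8 | 509 / 69.0 | 519 / 66.3 |
| #7 | 503 / 60.5 | 502 / 60.7 | 512 / 57.1 | 522 / 53.9 |

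\* Power essentially unchanged, at most 2 points above stated. Type I error stays at 1.9-2.1%.

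**The plan's figures are reproduced first.** With no lag, all seven rows agree with Table 3. A separately programmed run (8,000 trials per scenario) also agrees, and gives 91.2% power at a uniform 0.34 against the stated figure of about 91%.

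**Effect of the lag.** In #1 the saving against 560 is stated as 560 - 376 = 184 patients; with the lag it is 560 - 412 = 148 down to 560 - 438 = 122. Power losses against Table 3 are 1.1-3.8 points (#3), 2.5-5.2 (#4), 1.9-4.8 (#5), 1.6-4.3 (#6) and 3.4-6.6 (#7).

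**Sensitivity.** With 111 at both looks, #1 averages 450 and #7 has 51.8% power. Leaving post-selection overrun unscaled at 35 then 70 gives #7 a power of 56.8% and an average N of 523.

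**Mechanism in #3 to #7.** A subgroup is first selected at the second look in 13-26% of simulated trials. Only 560 - 380 - 69 = 111, down to 560 - 380 - 111 = 69, subgroup-only places then remain. The plan's figure of 180 further patients concerns selection at the first look, where it is attainable, and is not disputed.

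**Null row (a separate matter).** Table 3 states an average N of 426 and 59.1% futility stops. With no lag, the relaxed rule gives 461 and 45%, and the single theta gives 477 and 37%. The lag moves 461 to 474-486, further from the stated value.

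**The case against.** Several points on the other side are fair.

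- **Small lag.** Scenarios #3 to #7 taken alone would also fit an overrun of about 20. Zero lag is identified by #1 and #2: an overrun of 20 already gives averages of 388 and 406, about 3% above the stated 376 and 393. The seven rows together fit only no lag, but that rests on these two.
- **Size of the power loss.** Table 3 used 5,000 trials, so its standard error on power is about sqrt(0.741 x 0.259/5000) = 0.6 points in #3. The 1.1-point loss there at the low overrun is within simulation noise. The losses in #4 and #7, and those at the high overrun, are not.
- **Assumed overrun.** Section 6.4 gives totals and a gradual start, not an accrual curve. The size is therefore a range; the direction is the same throughout.
- **Unstated pause.** The DSMB charter is an attachment that is not in these documents and could describe a pause. If so, Table 3 stands for #1 to #7, but the two-year projection shows no sign of allowing for it.
- **Null row.** The two futility statements can be read together, since section 6.1 says the maximum becomes random after selection. A third reading of the relaxed bound gives 399 and 66% futility stops, on the other side of the stated values, but it no longer fits #7 (476 and 53.1%). This shows an under-specified rule, not a proven error in that row.

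None of this removes the main point.

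**Conclusion.** The concern holds. Scenarios #1 to #7 describe a trial with nobody in follow-up at an interim, whereas the plan as written has a 90-day lag and states no pause. The main effect is on average sample size: 36-62 patients more in #1, 32-59 more in #2 and 6-23 more in #3 to #7. Power in #3 to #7 falls by roughly 1 to 7 points.

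The case for the adaptive design survives. In #7, for example, power is still 54-57% against 12.8% for the fixed design. Confidence is medium, because the overrun is inferred from section 6.4 and the figure of 35 at the first look is assumed. The failure to reproduce the null row is not a lag effect. It means that the futility rule used in the simulations cannot be confirmed from the text.

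**What to change.** 1. Re-run Table 3 with the 90-day lag and an accrual curve consistent with section 6.4, and restate average N, futility rate and power. Alternatively, state an enrollment pause at each look and add about 6 months (two 90-day pauses) to the projection in section 6.4.
2. For selection at the second look, state that remaining subgroup accrual is 560 minus the number already randomised when the restriction takes effect.
3. State that overrun patients who belong to the selected subgroup enter its later tests.
4. Give one post-selection futility rule, worded the same in section 6.1 and Appendix B, and recompute the null row under it.

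The cost is a re-simulation and slightly less favourable published figures, or about 6 months of extra enrollment time if a pause is chosen. The maximum of 560 does not change.

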3.7.1.2. Secondary Outcomes

Secondary outcome measures include: 1) safety as measured by the incidence of symptomatic intracranial hemorrhage (sICH) (SITS-MOST)²¹, neurological worsening (defined as a ≥ 4 -point

increase on the NIHSS score within 24 hours due to the stroke itself), mortality and groin (or arterial access site) hematomas, infections or any vascular injury caused by the endovascular procedure, 2) rates of recanalization (complete and partial) using the modified TICl system (score $\geq 2b$ defined as favorable reperfusion), 3) length of hospital stay, and 4) discharge location. 5) significant improvement of ≥ 8 points on NIHSS at 24 hours of presentation or an NIHSS of 0-1

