3.7.1.3. Imaging Outcomes

Imaging endpoints are: 1) infarct volume on MRI DWI sequence (or CT if MRI not feasible) 24 hours to 7 days after randomization; 2) lesion growth between the RAPID identified ischemic core on baseline imaging and the infarct volume; 3) successful reperfusion defined as DWI lesion volume minus $T_{max} > 6$ seconds greater than 50%; and 4) the proportion of subjects with recanalization of the primary arterial occlusive lesion. The technical efficacy of the endovascular procedure will be assessed by a modified Thrombolysis in Cerebral Infarction scores of 2b (50% to 75% reperfusion), 2c (>75% to 99% reperfusion) or 3 (complete reperfusion).²²

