Considering a prior assumption that the EVT effect is largest in the patients with good imaging profile and treated within the shortest time window, we assume that the highest effect of EVT will be observed in G1A. Then the effects get decreased gradually in G1B, G2A, G2B, G3A, and the lowest effect will be observed in G3B. According to this adaptive design, when a most promising subgroup needs to be selected at the time of interim (or final) analysis, we will compare the GLR statistic among five cumulative groups, that is, G1A, G1A+G1B (i.e., Group 1), G1A+G1B+G2A, G1A+G1B+G2A+G2B (i.e., Group 1+Group 2), and G1A+G1B+G2A+G2B+G3A.

Primary analysis: The primary endpoint is the distribution of scores on the modified Rankin Scale (mRS) at day 90. The null hypothesis will be tested at the interim and final analysis using a normal approximation of the Wilcoxon-Mann-Whitney test (the GLR test). The principle of the intention to treat will be applied for the primary analysis. An additional analysis of the primary endpoint will be the same rank-based analysis comparing the 90-day mRs distribution between treatment groups while stratifying for prognostically important covariates. We will use the Generalized Cochran-Mantel-Haenszel test (CMH) to evaluate whether there is a uniform shift on the mRS distribution from one group to the other after stratification. The CMH test will be stratified by these variables used in the covariate adaptive randomization. For age, NIHSS, treatment time window, and CTP core volume, we will consider them as continuous variables in this adjusted analysis.

Power and sample size considerations Based on prior reported data, the following distributions were projected on the mRS at 90 days in EVT and MM groups for SELECT 2 in the overall population.

	mRS at day 90							Total
	0	1	2	3	4	5	6	
Endovascular group	4%	8%	12%	16%	19%	13%	28%	100%
Medical group	1%	4%	9%	14%	19%	10%	43%	100%

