Secondary analyses: Our secondary endpoint is the proportion of patients with mRS 0-2 at day 90 (indicating functional independence). The difference in the proportions of patients with mRS 0-2 between treatment arms will be assessed using logistic regression. We will adjust for the variables we used in adaptive randomization program in the logistic regression model. Other secondary endpoints include (1) the safety outcomes measured by the incidence of sICH, neurological worsening, mortality, groin hematomas, infections or vascular injury, (2) infarct volume, lesion growth, successful reperfusion, and recanalization rate, (3) length of hospital stay, and (4) discharge disposition. The exploratory analyses on secondary outcomes will include descriptive statistics (mean [\pm standard deviation, SD] or median and interquartile range for continuous variables and frequency [percentage] for discrete variables) and appropriate test for secondary outcome variables between two groups. For binary outcomes (e.g., sICH, neurological worsening, mortality, groin hematomas, infections or vascular injury, successful reperfusion, recanalization), Chi-square or Fisher's exact test where appropriate will be used to compare the incidence between two treatment groups for large core patients. We will also apply the logistic regression model on these outcomes after adjusting for the variables we used in adaptive randomization program. The adjusted odds ratio (OR), as well as 95% confidence interval will be reported. For the length of stay, mean \pm SD and median (Interquartile range) will be calculated for each group. For continuous variables (e.g., the length of stay and infarct volume), two sample t-test or Wilcoxon rank sum test as appropriate will be applied to compare them between two groups. For discharge disposition, frequency and percentage of each disposition will be reported and Chi-square test or Fisher's exact test where appropriate will be applied to compare its distribution between two groups.

Subgroup analyses: Subgroup analyses of the effect of thrombectomy on the primary and secondary endpoints will be performed. Subgroups will be defined based on the stratification variables, key demographic factors (such as race and ethnicity), thrombolysis vs. no thrombolysis, CTP vs. MRI selection, and witnessed vs. unwitnessed symptom onset, wake-up vs non-wake-up stroke, and TIC1 0-2a vs. TIC1 2b/3 results in the cath lab. An additional

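### Follow-up infarct volume is tested without adjustment for baseline core volume, which costs precision but not validity; length of stay also lacks a rule for death before discharge.

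*Combined protocol and SAP*

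**What the plan says.** **Infarct volume.** Section 6.1 (Secondary analyses) gives the whole inferential plan for comparing the arms on continuous secondary outcomes: "For continuous variables (e.g., the length of stay and infarct volume), two sample t-test or Wilcoxon rank sum test as appropriate will be applied". Covariate adjustment is promised for mRS 0-2 and, after a list of binary outcomes, in the sentence "We will also apply the logistic regression model on these outcomes after adjusting for the variables we used in adaptive randomization program". No adjusted model is named for a continuous outcome.

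**Baseline core volume is used elsewhere.**
- Section 3.1: patients have CT or MR perfusion processed by RAPID at presentation.
- Appendix A: core volume is a minimization factor in three bands.
- Section 6.1 (Primary analysis): core volume enters the adjusted analysis of the mRS as a continuous variable.
- Section 3.7.1.3: a separate imaging outcome is "lesion growth between the RAPID identified ischemic core on baseline imaging and the infarct volume". Section 6.1 lists it beside infarct volume.

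**Length of stay.** Section 3.7.1.2 includes "3) length of hospital stay, and 4) discharge location" among the secondary outcomes. Section 6.1 summarizes stay by mean, SD, median and IQR and applies the same t or Wilcoxon test. Neither section says what value a patient who dies before discharge receives. Section 6.5 deals only with a missing 90-day mRS.

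**The concern.** Baseline core volume is likely to predict final infarct volume, and eligible patients range from below 50cc to above 100cc. The plan balances on it at randomization and adjusts for it in an analysis of the primary endpoint, then drops it from the outcome to which it is most directly related. The cost is avoidable noise in one of the trial's main mechanistic readouts.

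Length of stay raises a different issue. If time from admission to discharge or death is tested as it stands, an early death is recorded as a short stay. The plan projects more deaths on medical management (MM) than on endovascular thrombectomy (EVT). A survival benefit could then appear as a longer stay with EVT, and a handling rule chosen after unblinding would be open to challenge.

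**Working it through.** **1. The plan's own figure.** No power or sample size is stated for infarct volume or length of stay. The mortality projections come from the Section 6.1 table ("the following distributions were projected on the mRS at 90 days in EVT and MM groups"), which supports the fixed-design total of 376. That total reproduces:
- P(EVT better) plus half the ties = 0.59375.
- Noether formula: N = (1.960 + 1.282)² / [12 × 0.25 × 0.09375²] = 398.5.
- Tie correction: 1 − Σp̄³ = 0.942, where p̄ is the mean of the two arms' category proportions. N = 398.5 × 0.942 = 375.4, rounded up to 376.

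**2. Infarct volume.** Let r be the correlation between baseline core and final volume on the analysis scale. The documents do not give it, so 0.4 to 0.7 is assumed. Relative to the unadjusted comparison:
- ANCOVA variance factor: 1 − r².
- Lesion growth as a change score, with equal variances at the two times: 2 − 2r.
- Power, for an effect that the unadjusted test detects with 80% power: Φ[(1.96 + 0.842)/√(variance factor) − 1.96].

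| r | ANCOVA variance | Power | Change-score variance | Power |
|---|---|---|---|---|
| 0.4 | 0.84 | 86.4% | 1.20 | 72.5% |
| 0.5 | 0.75 | 89.9% | 1.00 | 80.0% |
| 0.6 | 0.64 | 93.8% | 0.80 | 88.0% |
| 0.7 | 0.51 | 97.5% | 0.60 | 95.1% |

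The change score never does better than ANCOVA, because (2 − 2r) − (1 − r²) = (1 − r)², which is not negative. Below r = 0.5 it is less precise than the unadjusted test.

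**3. Length of stay.** At the maximum of 280 per arm, the projections imply 280 × 0.43 = 120 deaths on MM and 280 × 0.28 = 78 on EVT by day 90. These are upper limits for deaths before discharge.

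The plain Wilcoxon test was simulated with 1,000 trials per setting. Assumptions: survivors' stay identical in both arms, lognormal with median 8 days and log-SD 0.7. The table shows how often the test declares EVT stay longer, against 2.5% expected in that direction.

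| Share of 90-day deaths in hospital | Median stay at death 3 days | 4 days | 6 days |
|---|---|---|---|
| 40% | 13.4% | 9.1% | 4.3% |
| 60% | 24.5% | 13.8% | 6.2% |
| 80% | 40.8% | 26.2% | 6.2% |

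If patients who die stay as long as survivors, the rate returns to 2.5% to 3%. A second simulation used a survivors' median of 10 days, 25% to 100% of deaths in hospital, and 1,500 trials per setting. Total two-sided rejection ran from about 5% (deaths staying as long as survivors) to 67% (all deaths in hospital, median stay at death 3 days).

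Giving in-hospital deaths the worst rank does not restore the nominal rate. With identical survivor stays and the 40% to 80% range, it favors EVT in about 22% to 73% of trials.

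**The case against.** Several points on the other side are sound.

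- **Baseline core is not ignored.** A reader might infer that from the infarct-volume test alone. The documents use it in minimization, in the adjusted primary analysis and in lesion growth. Only the infarct-volume test omits it.
- **The infarct-volume test is not biased.** Randomization makes the unadjusted comparison valid, so the loss is efficiency alone. At r = 0.4 the gain is from 80% to 86%. At r = 0.7 lesion growth already reaches 95%, against 97.5% for ANCOVA.
- **The plan does not say that deaths count as short stays.** It is silent. That result follows only if raw time to discharge or death is tested.
- **43% and 28% are not in-hospital mortality.** They are projected mRS 6 rates at 90 days.
- **The length-of-stay distortion depends on the estimand.** If the target is bed-days used, a longer EVT stay caused by better survival is a real difference. Its size rests on three inputs that the documents do not give: survivors' stay, the in-hospital share of deaths, and stay at death.
- **The consequences are limited.** Section 6.1 labels these analyses exploratory and compares mortality and discharge disposition separately. No efficacy bound or stopping rule uses either outcome.

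Two things remain. Lesion growth does not replace adjustment, since it never improves on ANCOVA and does worse than the unadjusted test when r is below 0.5. And the absence of any stated handling of death is a gap under every estimand.

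**Conclusion.** The point holds as a free improvement in precision. For an assumed r of 0.4 to 0.7, adjusting infarct volume for baseline core removes 16% to 49% of the variance and turns 80% power into 86% to 98%. The documents support no claim that the planned test is invalid, and the primary conclusion is unaffected.

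Length of stay is a secondary point. The plan needs a stated rule for death before discharge. Under the first set of assumptions, a raw test wrongly signals longer EVT stay in about 4% to 41% of trials if the target is survivors' stay. That range is too dependent on undocumented inputs to carry the point, and the documents do not make one handling the only correct one.

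**What to change.** **Infarct volume.** In Section 6.1, make the main analysis an ANCOVA on a prespecified scale, such as log volume, with arm and continuous baseline RAPID core volume. Keep the unadjusted test as supportive. The sub-50cc band has no lower limit, so the SAP should say how zero or near-zero volumes are transformed. Follow-up scan timing (24 hours to 7 days) and modality (MRI, or CT where MRI is not feasible) arise after randomization and may depend on how the patient fares. They belong in a sensitivity analysis, not in the main model.

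**Length of stay.** State the estimand and one handling of death before discharge, for example death as a competing event for discharge alive. Report length of stay beside the number of in-hospital deaths in each arm. Worst-rank scoring is possible, but it would mostly repeat the mortality comparison.

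**Cost.** A few sentences of SAP wording and minor programming. Baseline core volume is already collected. The length-of-stay choice is a trade-off, because any measure that counts death also carries the mortality difference.
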